## **2.2 Suberoylanilide Hydroxamic Acid (SAHA)**

Suberoylanilide hydroxamic acid (SAHA; NSC 701852) is a small molecule inhibitor of histone deacetylase (HDAC) that binds directly in the enzyme's active site in the presence of a zinc ion (19). Because aberrant HDAC activity has been implicated in a variety of cancers, development of HDAC inhibitors is a rational approach to the design of targeted anticancer

therapeutics. Several HDAC inhibitors from multiple chemical classes have been developed and are currently in clinical trials. Trichostatin and butyric acid were among the first HDAC inhibitors to be administered to patients, but these were found to be clinically unsuitable due to potency and formulation issues (20,21). Depsipeptide was originally selected for clinical study based on its antiproliferative effects; subsequently it was discovered to antagonize HDACs (22) and was the first HDAC inhibitor to demonstrate clinical efficacy (23). Of the three classes of HDACs, SAHA targets most human Class 1 (related to the yeast transcriptional regulator Rpd3) and Class 2 (similar to the yeast Hda1) enzymes (24,25); the third class of HDACs (homologues of yeast sir2) requires NAD+ for activity and is not inhibited by SAHA. Among those currently in clinical trials, SAHA is the most potent HDAC inhibitor that can be administered orally with excellent bioavailability.

### **Mechanism of Action**

The HDACs exert their targeted action during post-translational acetylation of core nucleosomal histones, which affects chromatin structure, thereby regulating gene expression. DNA that is wrapped around condensed, non-acetylated histones is transcriptionally inactive, whereas acetylation of N-terminal histone lysine residues exposes DNA to important transcription factors that promote transcriptional activity (26,27). The dynamic equilibrium between histone acetylation and deacetylation is regulated by histone acetyltransferases (HATs) and HDACs. The action of HDACs on nucleosomal histones leads to tight coiling of chromatin and silencing of expression of various genes, including those implicated in the regulation of cell survival, proliferation, differentiation, and apoptosis (28). The effects of HDACs are not limited to histone deacetylation. HDACs also act as members of a protein complex to recruit transcription factors to the promoter region of genes, including those of tumor suppressors, and they affect the acetylation status of specific cell cycle regulatory proteins (27).

### **Nonclinical Activity**

SAHA was identified originally by its ability to induce differentiation of murine erythroleukemia cells at micromolar concentrations (29,30). Subsequently, it was found to induce differentiation or arrest growth of a wide variety of human carcinoma cells. To date, SAHA activity has been reported in transformed hematopoietic cells, such as multiple myeloma (MM) (31-33), acute promyelocytic leukemia (APL) (34), acute lymphocytic leukemia (35), chronic myelogenous leukemia (36,37), Waldenström's macroglobulinemia (33), and cutaneous T-cell lymphoma (CTCL) (38). Activity has also been reported in cell lines representing other tumor types including bladder transitional cell carcinoma (39), breast cancer (40-42), prostate cancer (43), head and neck squamous carcinoma (44), and colon carcinoma (45).

The antitumor activity of SAHA was demonstrated in several *in vivo* models of cancer, including a xenograft model of human CWR22 prostate cancer cells (43), a mouse model of APL containing the promyelocytic leukemia zinc-finger-retinoic acid receptor  $\alpha$  fusion gene (PLZF-RAR $\alpha$ ) (46), and an *N*-methylnitrosourea-induced mammary tumor model in rodents (47).

SAHA has also showed activity when administered daily by intraperitoneal (IP) injections in the CWR22 and PLZF-RAR $\alpha$  models and by oral (PO) administration in the carcinogen-induced mammary tumor model.

### **SAHA Combination Studies**

Accumulating evidence has demonstrated the effectiveness of HDAC inhibitors in combination with several other agents *in vitro*. The combination of SAHA and DNA hypomethylating agents (5-azacytidine or decitabine) acts synergistically to induce apoptosis, differentiation, and/or cell growth arrest in various cancer cell lines (48,49). When SAHA was combined with the anti-metabolite 5-fluorouracil, a supra-additive to additive antiproliferative effect in wild type and mutant-p53 colorectal cancer cells was observed (50). SAHA with imatinib mesylate (Gleevec®) may be effective in chronic myelogenous leukemia (CML) cells that resist imatinib mesylate through increased Bcr-Abl expression (36,37). Minimally toxic concentrations of the proteasome inhibitor bortezomib combined with SAHA resulted in increased apoptosis in human leukemia cells (37). In cells from RAR $\alpha$ -PLZF/RAR $\alpha$ -PLZF transgenic mice and in cells harboring t(15;17) (RAR $\alpha$ -PML fusion genes), SAHA induced significant apoptosis and growth inhibition, effects that were increased by adding all-*trans* retinoic acid (46). Pre-treating four human cancer cell lines (including a brain tumor line) with SAHA increased the killing efficiency of etoposide, ellipticine, doxorubicin, or cisplatin, but not of the topoisomerase I inhibitor camptothecin (51). However, treating cells in the reverse order (anticancer drug followed by SAHA) was no more cytotoxic than the anticancer drug alone. Finally, overexpression of Bcl-2 or Bcl-XL in leukemia and MM cell lines abolished SAHA-induced apoptosis but did not affect its differentiation or cell cycle regulatory effects (45,52,53). This suggests that agents blocking Bcl-2 expression or function could be effectively combined with SAHA. Studies done with other HDACs have suggested that a consequence of HDAC inhibitor-induced heat shock protein 90 (Hsp 90) acetylation is depletion of the Hsp 90 client protein Her-2 and increased apoptosis of breast cancer cell lines induced by taxotere, trastuzumab, epothilone B, and gemcitabine (54,55). In addition to these potentially additive or synergistic interactions between SAHA or other HDACs and various anticancer drugs, SAHA has shown synergistic activity when combined with radiotherapy in prostate cancer cell spheroids (56).

### **Phase 1 Clinical Experience**

A phase 1 study evaluated vorinostat administered intravenously (IV) to patients with advanced solid tumors and hematologic malignancies (57). Vorinostat was administered using two schedules: 2-hour IV infusion daily x 3 q21d, or daily x 5 for 1 to 3 weeks. No dose-limiting toxicities (DLTs) were observed in eight patients administered vorinostat daily x 3 q21d at doses of 75, 150, 300, 600, and 900 mg/m^2/day. One solid tumor patient given 900 mg/m^2 on the daily x 5 schedule for 3 weeks developed acute respiratory distress and grade 3 hypotension. Among five other patients at this dose, no additional DLTs were observed. Among 12 hematologic and 17 solid tumor patients enrolled on the daily x 5 schedule (300, 600, and 900 mg/m^2/day), therapy was delayed for 1 week for grade 3/4 leukopenia and/or thrombocytopenia in two of five patients with hematologic malignancies given 600 mg/m^2 for 3 weeks. The

maximum tolerated dose (MTD) for hematologic malignancy patients was 300 mg/m^2 daily x 5 for 3 weeks. An MTD for solid tumors was not determined because the study was terminated when an oral formulation became available. The mean terminal half-life ( $t_{1/2}$ ) ranged from 21 - 58 minutes, and the dose was linearly proportional to the area under the concentration versus time curve (AUC). Acetylated histones were detected in peripheral blood mononuclear cells (PBMCs) up to 4 hours post-infusion at higher dose levels. This observation was confirmed by immunohistochemical analyses of post-therapy tumor biopsies. Four patients, including two with lymphoma and two with bladder cancer, experienced objective tumor regression with clinical improvement in tumor-related symptoms.

As of 29-May-2009 the clinical safety of vorinostat is supported by data from 854 patients (858 patient-exposures) who have been treated in Merck & Co., Inc sponsored Phase I, II, and III studies (Investigator's Brochure, 2009) conducted in patients with both hematologic malignancies and solid tumors. An additional 290 patients were enrolled in a randomized, blinded study where patients are randomized in a 1:1 fashion to vorinostat or placebo. Merck & Co., Inc., including Banyu (Japan), has sponsored 30 vorinostat studies that are completed (11), closed (3), or ongoing (14). The NCI is working in collaboration with Merck & Co., Inc. to further evaluate vorinostat. The NCI-sponsored studies of vorinostat are in progress or are planned in a variety of different indications both in hematologic malignancies as well as solid tumors. To date, 1,230 patients have received vorinostat as either monotherapy or combination chemotherapy in 43 studies sponsored by the NCI.

In addition, vorinostat is also being evaluated in studies initiated and sponsored by independent Investigators, both as monotherapy and as combination chemotherapy. As of 29-May-2009, 44 of these Investigator initiated studies have enrolled 326 patients. These active studies are enrolling and additional studies are planned.

Therefore, over 2,574 patients have received at least one dose of vorinostat in studies sponsored by either Merck and Co., Inc., the NCI or independent Investigators.

The total daily doses studied ranges from 200 mg to 900 mg. The tolerability of oral vorinostat appears to be determined by total daily dose and the length of consecutive days of dosing. The maximum tolerated dose (MTD) for continuous daily dosing without a rest period is 400 mg daily or 200 mg BID. The MTD for intermittent dosing is 300 mg BID x 3 consecutive days per week, or 250 mg TID x 14 consecutive days followed by a 7-day rest. Dose-limiting toxicities (DLTs) of single agent vorinostat were mainly non-hematologic (anorexia, dehydration, diarrhoea, and fatigue); hematologic toxicities are primarily anaemia and thrombocytopenia, most of which were mild to moderate. The majority of these DLTs occurred within the first month on oral vorinostat. The DLTs were manageable because these toxicities resolved quickly after drug administration was interrupted. The optimal dose, dose frequency, and dose duration remains under active investigation.

The pharmacokinetics and toxicokinetics of vorinostat have been evaluated in

mice, rats, dogs and humans. Rapid oral absorption has been noted in all species studied. Vorinostat (0.5 to 50 µg/mL) exhibited moderate reversible binding to plasma proteins. In human plasma, vorinostat appears to bind primarily to human serum albumin; however, some binding of vorinostat was also observed in solutions of human  $\alpha$ 1-acid glycoprotein.

Vorinostat is excreted exclusively as metabolites, the majority of metabolites are derived from glucuronidation and hydrolysis with  $\beta$ -oxidation pathway metabolites accounting for the rest. As vorinostat is not eliminated via cytochrome P450 pathways, it is anticipated that vorinostat will not be subject to drug-drug interactions when co-administered with drugs that are known to be CYP inhibitors. Although vorinostat was not a potent reversible inhibitor of the cytochrome P450 isozymes ( $IC_{50} > 75 \mu M$ ), gene expression studies detected some potential for suppression of CYP2C9 and CYP3A4 activities at  $\geq 10 \mu M$  vorinostat however, these changes were observed at concentrations higher than the pharmacologically relevant serum concentration of  $2 \mu M$  ( $C_{max}$ ).

Pharmacokinetic analysis of 26 patients has indicated that the bioavailability of oral vorinostat is approximately 46%. Vorinostat doses in the range of 200 - 600 mg produced maximum concentration ( $C_{max}$ ) and drug exposure (AUC) curves that were linearly proportional. The  $t_{1/2}$  of oral vorinostat ranges from 92 to 150 minutes, and preliminary data suggest that administration of vorinostat with food does not appear to substantially alter the rate or extent of absorption. Inhibition of HDAC activity was achieved in PBMCs at the 200 mg dose level. At dose levels of 400 and 600 mg, the duration of HDAC inhibition lasted  $\geq 10$  hours.

Significant antitumor activity has been observed among members of the above patient trial population. In a phase 1 study of oral vorinostat, seven patients with heavily pre-treated diffuse large B-cell lymphoma were entered. Among these patients, one complete response (CR) and one partial response (PR) were observed. In addition, one patient has had a significant PET scan response. The PR lasted 5 months, the PET scan response lasted 6 months, and the CR was ongoing with a duration  $> 12$  months at last report. Decrease in tumor mass, pleural effusion, and improvement of tumor-related pain or shortness of breath have also been observed in patients with mesothelioma. In an ongoing phase 2 study of vorinostat in patients with heavily pretreated CTCL or peripheral T-cell lymphoma, objective responses have been observed (including PRs in 5 of 13 patients), and 8 of 10 patients reported decreased pruritus.

Zolinza® (vorinostat) was approved by the U.S. Food and Drug Administration (FDA) on 06-Oct-2006 for the treatment of cutaneous manifestations in patients with cutaneous T-cell lymphoma (CTCL) who have progressive, persistent or recurrent disease on or following two systemic therapies. Phase I and II clinical studies of Vorinostat sponsored by Merck & Co., Inc., Banyu (Japan), and the NCI have demonstrated confirmed anti-tumor activity in patients with acute myeloid leukemia (AML), advanced multiple myeloma, B-cell non-Hodgkin's lymphoma, squamous cell laryngeal carcinoma, thyroid carcinoma, breast carcinoma, non-small cell lung carcinoma, glioblastoma multiforme, and myelodysplastic syndrome.

## Potential for Drug Interactions

Vorinostat has a low propensity to cause or be affected by drug-drug interactions. In vivo animal models and in vitro human systems have demonstrated that the major pathways of metabolism of vorinostat involve glucuronidation, and hydrolysis followed by  $\beta$ -oxidation (Investigator's Brochure, 2009). As vorinostat is not eliminated via cytochrome P450 (CYP) pathways, it is anticipated that vorinostat will not be subject to drug-drug interactions when co-administered with drugs that are known to be CYP inhibitors or inducers. Since vorinostat was neither a potent inhibitor nor an inducer of CYP enzymes, drug-drug interactions caused by vorinostat are not anticipated. Additionally, vorinostat is not recovered intact in urine to any appreciable extent. Therefore, compounds known to affect renal elimination are not expected to affect the pharmacokinetics of vorinostat.

Prolongation of prothrombin time (PT) and International Normalized Ratio (INR) were observed in patients receiving vorinostat concomitantly with coumarin-derivative anticoagulants. Physicians should carefully monitor PT and INR in patients concurrently administered vorinostat and coumarin derivatives.

Vorinostat should not be administered concomitantly with other HDAC inhibitors (e.g., valproic acid) as class-specific adverse reactions may be additive. Severe (Grade 4) thrombocytopenia with associated gastrointestinal bleeding and anaemia has been reported with the concomitant use of vorinostat and valproic acid.

Patients who have received HDAC inhibitors or compounds with HDAC inhibitor like activity, such as valproic acid, for anti-neoplastic therapy should not enroll in vorinostat oncology trials. Patients who have received such agents for other indications, e.g. epilepsy, may enroll on vorinostat trials after a 30-day wash-out period.

## 2.3 FDG PET/CT

Assessment of tumor response to therapy plays a central role in drug development as well as clinical patient management. Currently response is mainly evaluated by measuring tumor size in CT and classifying tumor shrinkage according to standard criteria, such as those of the World Health Organization (WHO) or Response Evaluation Criteria for Solid Tumors (RECIST) 1.1 criteria (58-60). However, response rates as assessed by these criteria are not well correlated with patient survival. Furthermore, response is evaluated not earlier than 2-3 months after start of therapy. This represents a significant clinical problem, since many treatment regimens are only active in the minority of the patients, meaning that the majority of patients undergo prolonged therapy without benefits. Several studies have suggested that positron emission tomography (PET) with the glucose analog fluorodeoxyglucose (FDG) may be used to monitor tumor response very early in the course of therapy. Quantitative changes in tumor FDG uptake 2-3 weeks after start of therapy have been shown to correlate well with subsequent tumor shrinkage and patient survival in some tumor types (table 1). Conversely, the absence of a measurable decrease in tumor FDG uptake after the first chemotherapy cycle has been found to predict lack

of tumor shrinkage and poor patient survival.

| Table 1: Prognostic relevance of quantitative changes in tumor FDG uptake during chemo- or chemoradiotherapy |               |             |          |                 |                        |                      |                |
|---|---------------|-------------|----------|-----------------|------------------------|----------------------|----------------|
| Tumor  | Author | Year | N | criteria | median survival |                      | p-value |
|   |               |             |          |                 | responder       | non-responder |                |
| Esophagus   | Weber(61)     | 2001        | 37       | -35%            | >48                    | 20                   | 0.04           |
|   | Wieder(62)    | 2004        | 22**     | -30%            | >38                    | 18                   | 0.011          |
| Gastric   | Ott(63)       | 2002        | 35       | -35%            | >48                    | 17                   | 0.001          |
| Head and Neck   | Brun(64)      | 2002        | 47**     | median*         | >120                   | 40                   | 0.004          |
| Ovarian   | Avril (65)    | 2005        | 33       | -20%            | 38                     | 23                   | 0.008          |
| Lung  | Weber(65)     | 2003        | 57       | -20%            | 9                      | 5                    | 0.005          |
|   | Hoekstra (66) | 2005        | 56       | -35%            | 43                     | 18                   | 0.04           |

\* Median metabolic rate at the time of the follow-up study.

\*\* Chemoradiotherapy, otherwise chemotherapy.

Thus, FDG-PET has the potential to improve patient management by signaling the need for early therapeutic changes in non-responders, thereby avoiding the side effects and costs of ineffective treatment. Furthermore, as an early indicator of clinical benefit, FDG-PET may also facilitate oncologic drug development by shortening Phase II trials and detecting clinical benefit earlier in Phase III investigations.

An exploratory objective of this study (pending funding) will be to assess the association between a metabolic response after one and two cycles of chemotherapy and subsequent best tumor response according to standard anatomic response evaluation criteria (RECIST 1.1). The PET studies will be optional.

## **Rationale for Studying the Time Course of Tumor FDG Uptake During Chemotherapy**

To the best of our knowledge, there is very few data published on the use of PET scans to monitor response in ACC (67,68). Non small cell lung cancer (NSCLC) was chosen as a model because the data on this tumor type is more mature and abundant.

A previous study has indicated that, in patients with advanced NSCLC, changes in tumor FDG uptake after one cycle of chemotherapy are well correlated with patient survival (65). In addition, a study evaluating neoadjuvant chemotherapy has also shown that metabolic activity after one chemotherapy cycle is highly predictive of patient survival (66). A second study in patients undergoing neoadjuvant chemoradiotherapy retrospectively analyzed PET scans of patients with locally advanced NSCLC imaged after three cycles of induction chemotherapy and after completion of chemoradiotherapy (45 Gy) (69). Changes in tumor FDG uptake at both time points were predictive of patient survival. However, most of the patients underwent only two and not three PET studies. There are some data in locally advanced breast and esophageal cancer that PET imaging after one cycle of chemotherapy may be a slightly better predictor of patient survival than PET after 2-6 cycles (62,70,71).

Both patients treated in the NCI protocol 8057 ([section 2.4](#)) experienced subjective clinical and/or laboratorial improvement around 2-3 weeks after starting treatment with vorinostat. Therefore, this trial will measure changes in tumor FDG uptake after one and two cycles of chemotherapy.

### **Definition of a Metabolic Response in FDG-PET**

Based on the reproducibility of the FDG-signal in untreated tumors, relative changes of approximately 20% are very unlikely to be due to measurement errors or spontaneous fluctuations of tumor metabolic activity (72,73). These data establish the minimal effect of treatment on tumor metabolic activity that can be assessed by FDG-PET. However, a measurable change in metabolic activity does not necessarily imply that treatment has a beneficial effect for the patient. A recent study evaluated the prognostic implications of a measurable change in tumor glucose utilization in patients with advanced NSCLC, who were treated with palliative platinum-based chemotherapy. A "metabolic response" in PET was prospectively defined as decrease of the SUV of the primary tumor by at least 20%. A total of 57 patients were included in the study and 28 tumors showed a metabolic response after the first chemotherapy cycle. Median progression-free survival of metabolic nonresponders was only 1.8 months versus 5.9 months for metabolic responders. Median overall survival of metabolic responders was 8.4 months and only 5.0 months for metabolic nonresponders (65). The sensitivity and specificity of a metabolic response for prediction of best response according to RECIST criteria were 95% and 74%, respectively.

These data indicate that a measurable change in tumor FDG uptake after the first cycle of chemotherapy is associated with a palliative effect of therapy. These data and the data on the test-retest reproducibility of FDG-PET suggest that a 20% decrease in tumor FDG uptake may be

used to define a metabolic response in patients with NSCLC. However, we will use slightly stricter criteria for a metabolic response in the present study and define a metabolic response as a decrease of tumor FDG uptake by 25%. The rationale for this definition is that the test/retest reproducibility of FDG-PET in a multicenter trial may be lower than previously reported in single-center studies. Therefore, a 20% threshold may not be robust enough for a multicenter trial. Defining a metabolic response as a 25% decrease of tumor FDG uptake makes this study also consistent with previous recommendations by the EORTC (74).

Although data in the literature support the use of a 25% decrease in tumor FDG uptake as a criterion for a metabolic response, we cannot exclude that other threshold values may allow a better prediction of patient outcome. Therefore, receiver operating characteristic (ROC) curves will be calculated for prediction of best response by quantitative changes in FDG uptake after one and two cycles of chemotherapy. Predictive accuracy will be evaluated through 95% confidence intervals for the area under the ROC curve (75)

All PET/CT data will follow the guidelines specified in appendices B and C (76) .

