#### **Treatment Period:**

Vorinostat will be administered orally once daily continuously at 400 mg. Each treatment cycle will consist of 4 weeks of daily treatment.

Study visits will be conducted on weeks 2 and 4 ( $\pm 1$  day) for the first cycle, then for the second cycle on week 5 and 7, ( $\pm 1$  day); then from week 9 on, every four weeks ( $\pm 1$  day) thereafter for the remainder of the study. Patient medical histories, physical examinations, laboratory tests, assessments of compliance with study medication and recording of adverse events will be conducted during study visits. Further blood may be drawn for research correlatives. For patients that have been on study longer than 2 years, office visits can be done every 12 weeks ( $\pm 7$  days), with medical history, concurrent meds, physical exam, vital signs, weight, performance status, and adverse events evaluation done also at that time. For patients that have been on study longer than 2 years, hematology labs and serum chemistry can be done every 6 weeks ( $\pm 7$  days).

The severity duration and relationship to vorinostat will be determined for each adverse experience (AE) ([Section 11](#)).

Blood will be drawn on days 1 prior to first drug intake, and on days 7 (+- 1 day) and 28 (+- 1 day), prior to drug intake, to assess for correlative studies.

Patients will have radiological tumor assessment by computed tomography (CT) scan (or magnetic resonance imaging - MRI) on days -14 to -1 (prior to the start of vorinostat) and day 56 ( $\pm 3$  days). They will be followed with CT scans or MRI every 2 cycles / 8 weeks ( $\pm 1$  week) thereafter. Patients may receive scans every 3 cycles/12 weeks ( $\pm 1$  week) after completing 6 months of treatment on study. Patients that have been on study longer than 2 years can have tumor measurements (CT scans or MRI) done every 24 weeks ( $\pm 10$  days).

Predicated on obtaining funding, additional scans (optional) will be performed. These will include PET/CT scans prior to treatment, Day 28 ( $\pm 3$  days), and Day 56 ( $\pm 3$  days). An additional CT scan or MRI will also be performed on Day 28 ( $\pm 3$  days) for comparison purposes. The Day 28 CT/MRI and the PET/CT scans will be optional studies- due to financial issues (funding).

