| Tumor measurements p               | X c             | Tumor measurements are repeated every 8 weeks ( $\pm$ 1 week) for the first 6 cycles. After 6 months on study, can be performed every 12 weeks ( $\pm$ 1 week). Documentation (radiologic) must be provided for patients removed from study for progressive disease. Objective responses should be confirmed within 4 weeks. |                |      |                |                |      |                |      |                |          |                | X h |
| Archival tumor tissue collected               | X b             |  |                |      |                |                |      |                |      |                |          |                |                |
| Blood for correlative studies j, m |                            | X  |                |      | X              |                |      |                |      |                |          |                |                |

|   |                |  |  |  |                |  |  |  |                |  |  |  |  |  |
|---|----------------|--|--|--|----------------|--|--|--|----------------|--|--|--|--|--|
| PET/CT L   | X c |  |  |  | X i |  |  |  | X i |  |  |  |  |  |

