#### 10.1.4.3 **Evaluation of Best Overall Response**

The best overall response is the best response recorded from the start of the treatment until disease progression/recurrence (taking as reference for progressive disease the smallest measurements recorded since the treatment started). The patient's best response assignment will depend on the achievement of both measurement and confirmation criteria.

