## 12.4 Analysis of Secondary Endpoints

There are 5 Secondary Objectives:

- 1) To characterize the safety and tolerability of vorinostat in this patient population
- 2) To assess the time to response (TTR)
- 3) To assess the response duration (RD)
- 4) To evaluate progression free survival (PFS)
- 5) To assess overall survival (OS)

Secondary Objective 1 concerns toxicity and adverse events, hence will involve categorical variables. They will be tabulated via frequency distributions, and also dichotomized to report the proportion (and percentage) of patients experiencing a specified level (e.g., Grade 3-4) of toxicity. Analysis of these proportions (i.e., rates) will include both point and 90% confidence interval (CI) estimates, with the CI estimates calculated via Wilson's method. The 90% confidence level is appropriate for either the Stage 1 sample size (n=12) or even the Stage 2 sample size (n=29) planned for this Phase II trial.

Secondary Objective 2 concerns TTR, which is a continuous variable not subject to censoring. It will be summarized descriptively, reporting N, median, mean, standard deviation (SD), standard error (SE), minimum, maximum, and 90% CI for the mean calculated from the SE and asymptotic Normal distribution theory.

Secondary Objectives 3-5 concern censored time-to-event (TTE) endpoints. Their distribution will be estimated using standard survival analysis techniques, and the Kaplan-Meier (K-M) method. From the K-M life tables, both point and 90% CI estimates of various statistics of interest can be calculated (e.g., median, 6-month event-free rate, 12-month event-free rate, etc.). Statistical graphs of each K-M curve (with 90% CI lines) will be generated for visual display of these censored TTE endpoints.

There are 7 Exploratory Objectives:

- 1) To assess the association between a metabolic response by PET/CT after one cycle of chemotherapy and subsequent best tumor response according to standard anatomic response evaluation criteria (RECIST).
- 2) To assess the association between a metabolic response by PET/CT after the first and second chemotherapy cycle and PFS.
- 3) Flow sort diploid, aneuploid, and tetraploid populations of tumor cells from FFPE tissue blocks from patients who benefited from SAHA therapy and from patients who did not demonstrate a durable benefit.

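### The two-cycle PET ROC in Section 2.3 is called prediction, but the day-56 PET shares its window with the first mandatory CT/MRI, so its AUC mixes concurrent association with prediction

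*Combined protocol and SAP*

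**What the plan says.** - **Section 2.3, opening text.** The exploratory aim is the association "between a metabolic response after one and two cycles of chemotherapy and subsequent best tumor response according to standard anatomic response evaluation criteria". It names both PET time points and calls the outcome subsequent.
- **Section 2.3, definition of a metabolic response.** ROC "curves will be calculated for prediction of best response by quantitative changes in FDG uptake after one and two cycles of chemotherapy". The text adds: "Predictive accuracy will be evaluated through 95% confidence intervals for the area under the ROC curve".
- **Section 10.1.4.3.** "The best overall response is the best response recorded from the start of the treatment until disease progression/recurrence". The clock starts at treatment, not at the PET.
- **Schema, Treatment Period.** CT or MRI is done at baseline ("prior to the start of vorinostat) and day 56"), with a window of ±3 days on the latter. The optional PET/CT scans are at baseline, day 28 ±3 and day 56 ±3. A further CT/MRI at day 28 is also optional.
- **Section 9.** "Tumor measurements are repeated every 8 weeks", with a tolerance of one week.
- **Sections 1.3 and 12.4, Objective 1.** "To assess the association between a metabolic response by PET/CT after one cycle of chemotherapy and subsequent best tumor response". The analysis text in 12.4 uses the SUV change after one cycle only.
- **Section 12.4, Objective 2.** PFS is counted from after the second PET (day 28), and a similar analysis is planned for the third PET (day 56). No such starting point is given for best response.

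**The concern.** A predictive ROC needs the outcome to be open when the predictor is measured. For the day-56 PET, part of the outcome has been measured in the same week, sometimes on an earlier day. A fall in FDG uptake that only mirrors shrinkage visible on that week's CT would then count towards predictive accuracy.

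Section 2.3 presents PET as a way to signal non-response early and to shorten Phase II trials. That use needs PET to precede the anatomic result and to tell the investigator something that the CT does not. An AUC that pools settled and open outcomes cannot show this.

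There is also a plain mismatch. The two-cycle best-response ROC appears only in Section 2.3, so an analyst working from Section 12.4 cannot tell whether to run it or in which patients.

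**Working it through.** **1. Stated figures.** The plan gives no sample size, expected AUC or power for the ROC. The only figures to reproduce are those of the Simon design in 12.1.1 (12 then 29 patients, continue on ≥1 response, promising on ≥3).

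- Early termination at 5%: 0.95^12 = 0.540, as stated.
- P(promising | p) = Σ(x = 1 to 12) b(12, x, p) × P(Bin(17, p) ≥ 3 − x). This is 0.148 at p = 0.05 and 0.9005 at p = 0.20, consistent with the stated 0.15 and 0.90.

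The design is needed here only for expected responders among 29: 29 × 0.05 = 1.45 and 29 × 0.20 = 5.8.

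**2. Timing.**

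| Assessment | Window (days) |
|---|---|
| Two-cycle PET | 53–59 |
| First mandatory CT/MRI, Schema | 53–59 |
| First mandatory CT/MRI, Section 9 | 49–63 |

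The CT can precede the PET by up to 59 − 53 = 6 days under the Schema, or 59 − 49 = 10 days under Section 9. If days are assumed uniform and independent within the windows, the CT falls on or before the PET day in 28/49 = 57% of pairings (Schema) or 56/105 = 53% (Section 9).

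**3. What is settled at the day-56 CT.**

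| Status on that CT | Best response |
|---|---|
| PD | Settled. It is PD, or whatever the optional day-28 scan recorded first. The patient is a non-responder. |
| PR/CR criteria met | Provisional. Sections 10 and 10.1.4.3 require confirmation at least 4 weeks later, so day 53 + 28 = 81 to day 59 + 28 = 87. |
| SD | Open. Section 12.1.1 expects responses up to one year after the start of treatment. |

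Neither 2.3 nor 12.4 removes the first two groups from the ROC or requires the PET to come before the CT.

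**4. Possible size, under assumptions.** Let f be the share of eventual responders already meeting PR/CR criteria at day 56, and c the AUC of the same-time PET for them. Let the PET have no ability to identify later responders (AUC 0.5). Then AUC = f × c + (1 − f) × 0.5.

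| f | c = 0.80 | c = 0.95 |
|---|---|---|
| 0.25 | 0.575 | 0.613 |
| 0.50 | 0.650 | 0.725 |
| 0.75 | 0.725 | 0.837 |

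The formula sets 0.5 for later responders by assumption. A simulation relaxes this: the PET tracks same-day size but carries nothing further about later change. Assumptions: log size change to day 56 Normal with mean 0 to 0.03 and SD 0.18 to 0.22, PET–size correlation 0.4 to 0.8, overall response 14 to 20%. Then 14 to 28% of responders meet PR by day 56, and 15 to 23% of patients have PD.

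| Analysis of the day-56 PET | AUC | AUC, another later-growth assumption |
|---|---|---|
| As planned, all patients | 0.61–0.78 | 0.64–0.80 |
| Only patients still open at day 56 | 0.53–0.64 | 0.56–0.71 |
| Also allowing for same-day size | 0.50 | 0.50 |

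Restricting to open patients therefore removes only part of the inflation. Same-day size carries the rest, because a tumour that has already shrunk somewhat is closer to the PR threshold.

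**5. Precision.** Hanley–McNeil variance at AUC A = 0.70: Q₁ = A/(2 − A) = 0.538, Q₂ = 2A²/(1 + A) = 0.576.

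- 6 responders of 29: [0.21 + 5(Q₁ − 0.49) + 22(Q₂ − 0.49)]/(6 × 23) = 0.0171, so the 95% half-width is 1.96 × 0.131 = 0.26.
- 2 responders of 29: [0.21 + 1(Q₁ − 0.49) + 26(Q₂ − 0.49)]/(2 × 27) = 0.0464, so the half-width is 1.96 × 0.215 = 0.42.

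**The case against.** The governing section already does the right thing. Objective 1 in 1.3 and 12.4 uses the one-cycle PET, about four weeks before the first mandatory CT, and the day-56 PET enters 12.4 only for PFS, counted after the scan. The two-cycle ROC is background text for an optional analysis. The word subsequent in 2.3 could itself be read as the missing restriction. With at most 29 patients, the interval is wider than the bias: the gap between planned and restricted AUC in the first simulation is roughly 0.61 − 0.53 = 0.08 to 0.78 − 0.64 = 0.14, against half-widths of 0.26 to 0.42. All of this stands and limits the weight of the point. It does not remove it: a wide interval around a mislabelled quantity is still mislabelled, and one word does not define an analysis set.

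A reader might infer three stronger things that the documents do not support.

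- **That the day-56 outcomes are already known.** Only progression is final. A day-56 PR awaits confirmation, and even in the simulation 72 to 86% of responders appear later.
- **That a landmark alone would show whether PET adds to CT.** It would not: the restricted AUC stays above 0.50 when PET adds nothing.
- **That the ROC would justify early use of PET.** The early question belongs to the day-28 PET. There, only progression by day 28 or a finding on the optional day-28 CT/MRI overlaps.

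**Conclusion.** The point holds in a limited form. As written, Section 2.3 would report a partly concurrent association for the day-56 PET as predictive accuracy, and it extends the best-response analysis beyond Sections 1.3 and 12.4. Timing, the best-response definition and the mismatch all come from the text and need no assumption.

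The size does not come from the text. The documents give no SUV data, no distribution of size change and no PET–size correlation, so the AUC ranges above illustrate the mechanism and do not measure it. With 1.45 to 5.8 expected responders among 29 (Section 8 and Appendix D report two partial responses), one or two already visible at day 56 could drive the estimate. The effect is confined to one exploratory analysis that depends on funding. The primary endpoint and all secondary endpoints are untouched.

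**What to change.** Choose one of two courses and state it identically in 2.3 and 12.4.

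1. **Preferred, and simplest.** Limit the predictive best-response ROC in 2.3 to the one-cycle PET, matching 1.3 and 12.4. Report the day-56 PET against best response separately, labelled concurrent association.
2. **If a two-cycle predictive analysis is wanted.** Set a landmark at the PET, in the way 12.4 counts PFS after the scan. Include only patients without PR/CR or PD on any CT/MRI up to and including that PET window, and count only responses first documented later. Report the result beside the same-day CT size change, and do not claim from the landmark AUC alone that PET adds to CT.

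The cost is a wording change and, for the second course, one filter and one extra column in the table. No patient procedure changes. The second course leaves fewer responders and a wider interval in an analysis that is already imprecise, which is a reason to prefer the first.
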